The IDMC will review accumulating reactogenicity and safety data monthly throughout the period of vaccination (up to 30 days after administration of Dose 2 in Step 3, i.e. Day 60). The IDMC will also review incidence of all serious adverse events (SAEs) and incidence of RSV-respiratory tract infections (RTI), RSV-LRTI, RSV-severe LRTI and RSV-RTI leading to hospitalization monthly after the start of vaccination and from beginning of the first RSV season to the end of the study.

Both iSRC and IDMC will receive critical safety data (i.e. SAEs and adverse events of specific interest) within 48 hours upon GSK becoming aware of it.

The iSRC and IDMC will determine whether any of the predefined study holding rules are met. If this is the case, vaccination in the study will be immediately put on hold. At any time, the IDMC may recommend to the sponsor to suspend the enrolment to the study and/or vaccination based on the safety data regularly arising in this study.

Dose escalation will proceed after administration of the vaccine to all subjects in the previous *step if no significant* safety concern *is* detected by the IDMC in *their regular review* of accumulating safety data. *The IDMC may recommend for dose escalation to proceed in the absence of a concern based on safety data review on a minimum of 16 subjects completing dose 2. The IDMC may recommend that based on the evolving safety profile, sufficient information has been accumulated to allow safe progression to the next sequential dose level. Thus, the number of subjects enrolled to the low and mid dose is between 16 and 32 subjects but the number of subjects enrolled to the high dose remains fixed at 32 subjects. (Amended 10 December 2017)*

Additionally, the IDMC will perform a review when all safety data up to 30 days after administration of Dose 2 in Step 3 (i.e. Day 60) are available.

Objectives**Primary**

- To evaluate the safety and reactogenicity of three dose levels of the RSV investigational vaccine when administered as two IM doses according to a 0, 1-month schedule, up to 30 days after Dose 2 (i.e. Day 60) in RSV-seropositive infants aged 12 to 23 months.

Secondary

- To evaluate the safety of two IM doses of three dose levels of the RSV investigational vaccine when administered according to a 0, 1-month schedule from study start (Day 0) up to study conclusion (Day 730) in RSV-seropositive infants aged 12 to 23 months.

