3	RSV-Hd	~ 16	12 months - 23 months	x	x
	Placebo-Hd	~ 16	12 months - 23 months	x	x

RSV-Ld: low dose ChAd155-RSV vaccine (5×10^9 vp); **RSV-Md:** middle dose ChAd155-RSV vaccine (1.5×10^{10} vp); **RSV-Hd:** high dose ChAd155-RSV vaccine (5×10^{10} vp).

***The target will be to enroll up to 96 RSV-seropositive infants aged 12 to 23 months at the time of first vaccination (unless the dose escalation IDMC decision can be made based on the evaluation of accumulating safety data on fewer subjects) to ensure that at least 64 infants receive two doses of study vaccine (ChAd155-RSV or Placebo). Then the number of subjects at each step will be at least 16 (approximately 8 subjects per group) at steps 1 and 2 and 32 (approximately 16 subjects per group) at step 3 (Amended 10 December 2017)**

Synopsis Table 2 Study groups and treatment foreseen in the study

Treatment name	Volume administered	Vaccine/Product name	Study Groups						
			Step 1		Step 2		Step 3		
			RSV-Ld	Placebo-Ld	RSV-Md	Placebo-Md	RSV-Hd	Placebo-Hd	
ChAd155 5x10 ⁹ vp	0.5 ml	ChAd155-RSV	X						
ChAd155 1.5x10 ¹⁰ vp	0.15 ml	ChAd155-RSV			X				
ChAd155 5x10 ¹⁰ vp	0.5 ml	ChAd155-RSV					X		
Placebo 0.5	0.5 ml	Formulation buffer S9b		X					X
Placebo 0.15	0.15 ml	Formulation buffer S9b				X			

RSV-Ld: low dose ChAd155-RSV vaccine (5 x 10⁹ vp); **RSV-Md:** middle dose ChAd155-RSV vaccine (1.5 x 10¹⁰ vp); **RSV-Hd:** high dose ChAd155-RSV vaccine (5 x 10¹⁰ vp).

- Control: placebo control (Formulation buffer S9b).
- Vaccination schedule(s): two IM vaccine doses administered according to a 0, 1-month schedule (i.e. at Day 0 and Day 30).
- Treatment allocation: infants will be randomized using a randomization system on internet (SBIR) at first vaccination.
- Blinding: observer-blind in Epoch 001 and single-blind in Epoch 002 .

Synopsis Table 3 Blinding of study epochs

Study Epochs	Blinding
Epoch 001	observer-blind
Epoch 002	single-blind

- Sampling schedule:

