9.10.5. Holding rules

The safety holding rules which will be assessed by the investigator are defined in [Table 21](#) and the safety holding rules which will be assessed by the iSRC and the IDMC during the safety evaluation are defined in [Table 22](#).

Table 21 Holding rules assessed by the investigator

Holding Rule	Event	Number of infants/group		
		Step 1	Step 2	Step 3
1a	Death or any life-threatening serious adverse event (SAE) that can be causally related to vaccination, according to investigator's assessment.	≥ 1	≥ 1	≥ 1
1b	Any withdrawal from the study (by investigator or parent(s)/LAR(s) of the subject request) following a Grade 3 AE that cannot reasonably be attributed to a cause other than vaccination.	≥ 1	≥ 1	≥ 1
1c	Any local or general solicited AE leading to hospitalization that cannot reasonably be attributed to a cause other than vaccination.	≥ 1	≥ 1	≥ 1
1d	Within 30 days post-vaccination, Any spontaneous local or general bleeding AND Thrombocytopenia < 50000/mm ³	≥ 1	≥ 1	≥ 1

If an investigator detects one of the holding rules mentioned above, he/she will immediately put the enrolment or the vaccination on hold (refer to Section 9.10.6) and he/she will immediately inform the sponsor and enter the data in the eCRF. It is sponsor's responsibility to put the enrolment or the vaccination on hold at all sites.

Table 22 Holding rules during the planned iSRC and IDMC evaluation

Holding Rule	Event	Number of infants/group		
		Step 1	Step 2	Step 3
2a	Any Grade 3 solicited local AE lasting 48 hours or more in an investigational RSV vaccine group, within the 7-day (Days 0-6) post-vaccination period.	≥ 25% & ≥ 2 infants/group	≥ 25% & ≥ 2 infants/group	≥ 25% & ≥ 2 infants/group
2b	Any Grade 3 solicited general AE lasting 48 hours or more in an investigational RSV vaccine group, that cannot reasonably be attributed to a cause other than vaccination, within the 7-day (Days 0-6) post-vaccination period.	≥ 25% & ≥ 2 infants/group	≥ 25% & ≥ 2 infants/group	≥ 25% & ≥ 2 infants/group

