2c	Any ≥ Grade 3 unsolicited AE in an investigational RSV vaccine group, that cannot reasonably be attributed to a cause other than vaccination, within the 7-day (Days 0-6) post-vaccination period OR Any ≥ Grade 3 abnormality in pre-specified hematological or biochemical laboratory parameters in an investigational RSV vaccine group, if it cannot reasonably be attributed to a cause other than vaccination, up to the Day 7 post-vaccination visit ¹	≥ 25% & ≥ 2 infants/group	≥ 25% & ≥ 2 infants/group	≥ 25% & ≥ 2 infants/group

[figure not shown]
¹ Refer to [Appendix C](#).

Of note, no formal holding rules will be applied for other safety data collected. However, these data will also be reviewed by the iSRC and the IDMC in order to allow for an overall assessment of the benefit/risk ratio of vaccination.

Risk assessment

Figure 4 gives the probability of not meeting holding rule 1-2 for 16 subjects per study group in each step.

Figure 4 Evaluations based on 16 subjects - Risk assessment curve for one formulation based on the proposed safety holding rules

The above figure illustrates that, with *a maximum of* 16 subjects per study group (Amended 10 December 2017):

- Each holding rule 1 (a - d) has more than 85% chance of not being met for vaccination with a true incidence rate below 1% and has more than 80% chance of being met for vaccination with a true incidence rate above 10%.
- Each holding rule 2 (a - c) has more than 90% chance of not being met for vaccination with a true incidence rate below 10% and more than 60% chance of being met for vaccination with a true incidence rate above 25%.

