11.4. Determination of sample size

No hypothesis driven sample size calculation was conducted due to the nature of descriptive summary of the study objectives. The sample size of 32 subjects per dose cohort/Step, randomized 1:1 to vaccine or placebo, was based on conventional study designs for Phase 1/2 trials. Specifically, if no adverse event was observed among 16 RSV vaccinated subjects, the exact, two-sided 95% confidence interval (CI) would rule out an AE rate of 20% or more; if the incidence rate of AEs is more than 10%, there will still be more than an 80% chance of observing at least one subject with this AE. Combining all RSV vaccinees across all dose levels, there will be more than a 99% chance of observing at least one subject with this AE.

Furthermore, with 16 RSV vaccinees, the maximum width of a 95% CI for the proportion of subjects with adverse events among 16 vaccinees is about 50% (see [Figure 5](#)). (Amended 10 December 2017)

[Figure 5](#) illustrates the precision on the percentage of subjects with symptoms following vaccination.

Figure 5 Exact 95% confidence interval on the percentage of subjects with adverse events following vaccination for 16 subjects per group

Taking the a priori safety concern of thrombocytopenia, both Frequentist and Bayesian approaches will be applied here to provide complementary assurance on the possibility to exclude a signal based on the accumulated safety data. The Frequentist approach examines the statistical power to rule out a significant decrease in platelet counts due to vaccination that would suggest a four-fold or greater increase in the risk of a Grade 3 or higher thrombocytopenia with 16 subjects per dose cohort. The Bayesian approach calculates the posterior predictive probability of not observing any subject with a Grade 3 or higher thrombocytopenia among the future 16 subjects by basing it on what we have observed in the first 16 subjects.

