If we assume platelet counts in healthy infants between 12 and 23 months follow a normal distribution with a mean of 300,000 platelets/mm³ and a standard deviation of 75,000 platelets/mm³, then we would expect 0.04% of unvaccinated infants to have a count below 50000 platelets/mm³, which is the cut-off for a Grade 3 thrombocytopenia. To rule out a four-fold or greater increase, we would need to show that the mean platelet count does not fall below 190,000 platelets/mm³ with a standard deviation of 47,500. The sample size needed to rule out a 110,000 platelets/mm³ decrease due to vaccination with 84% power when vaccination has no effect on platelet count is 16 infants per dose cohort (8 per group). Sample size is based on a one-sided 0.025 test of non-inferiority using the Mann-Whitney statistic (PASS 12, Non-inferiority Tests for Two Means using Differences).

The Bayesian approach to predict the probability of no Grade 3 or higher thrombocytopenia in the future 16 subjects per dose cohort will be conducted by treating the mean of platelet counts μ as a random variable with a normal prior distribution $N(\mu_0, \sigma_0^2)$, where μ_0 and σ_0 will be determined by using laboratory normal

range. For this analysis the range of 150,000 to 450,000 platelets/mm³ will be the focus. Based on this laboratory range, μ_0 would be 300,000, a mean of the range, and σ_0 would be 75000, an approximate of a standard deviation of data sampled from this normal range. After 16 infants complete the two-dose vaccination schedule, a posterior distribution of μ will be calculated based on the prior of μ and the observed platelet counts from Day 31. The posterior predictive probability of no Grade 3 or higher thrombocytopenia in the future 16 subjects per dose cohort will be calculated, and sensitivity on the prior will be assessed.

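### Section 9.10.5 presents holding-rule probabilities computed for 16 per group as holding for a maximum of 16; at the 8 per group now permitted in Steps 1 and 2, rule 1 is met at a 10% rate with probability 57.0%, not above 80%

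*Protocol*

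**What the plan says.** Section 9.10.5 of the protocol states that Figure 4 "gives the probability of not meeting holding rule 1-2 for 16 subjects per study group in each step", and the figure's title also refers to 16 subjects. The bullets below it are introduced, since Amendment 4, as applying with *a maximum of* 16 subjects per study group. They make four statements:

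- Rule 1 (each of a to d): more than 85% chance of not being met at a true rate below 1%.
- Rule 1: "has more than 80% chance of being met for vaccination with a true incidence rate above 10" percent.
- Rule 2 (each of a to c): "has more than 90% chance of not being met for vaccination with a true incidence rate below 10" percent.
- Rule 2: more than 60% chance of being met at a true rate above 25%.

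Table 21 triggers rule 1 on one infant in a group. Table 22 triggers rule 2 on "≥ 25% & ≥ 2 infants/group".

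The same amendment changed the group sizes. The footnote to Synopsis Table 1, repeated under Table 1 in Section 3, says: "Then the number of subjects at each step will be at least 16 (approximately 8 subjects per group) at steps 1 and 2". For Step 3 the synopsis says that the number of "subjects enrolled to the high dose remains fixed at 32 subjects".

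**The concern.** For a rule triggered by a single event, the chance of meeting it rises with the number of vaccinees. A detection probability of more than 80% computed at 16 is therefore the best case over all sizes up to 16. Introducing it with *a maximum of* 16 presents that best case as a property of every permitted size.

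Rule 1 covers the gravest events: related death or life-threatening SAE (1a); withdrawal after a Grade 3 AE not reasonably attributable to a cause other than vaccination (1b); hospitalization for a solicited local or general AE not reasonably attributable to a cause other than vaccination (1c); and spontaneous bleeding with platelets below 50,000/mm³ within 30 days of vaccination (1d). This is the vaccine's first use in infants. Those who rely on the protocol, including the IDMC that reviews it, would take from Section 9.10.5 that a halved cohort detects such events as well as a full one.

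**Working it through.** **Inputs.** Group size behind the figures: 16 (Section 9.10.5). Permitted minimum in Steps 1 and 2: about 8 per group (footnotes to Synopsis Table 1 and Table 1; Section 6.2.2.2.1). Triggers: Tables 21 and 22. Infants are treated as independent with a common event rate p, so the number affected among n vaccinees is binomial.

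**Formulas.**
- Rule 1 met: 1 − (1 − p)^n. Rule 1 not met: (1 − p)^n.
- Rule 2 threshold: r = max(2, 0.25n rounded up). Rule 2 met: P(X ≥ r). Rule 2 not met: P(X ≤ r − 1).

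**The protocol's figures at n = 16.**
- Rule 1 not met at 1%: 0.99^16 = 85.1% (stated above 85%).
- Rule 1 met at 10%: 1 − 0.9^16 = 81.5% (stated above 80%).
- Rule 2 (r = 4) not met at 10%: P(X ≤ 3) = 93.2% (stated above 90%).
- Rule 2 met at 25%: P(X ≥ 4) = 59.5% (stated above 60% for rates above 25%; the gap is rounding and is not counted here).

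So the four statements are reproduced as calculations for 16 per group.

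**The same quantities at other sizes.**

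| Vaccinees n | Rule 1 not met at 1% | Rule 1 met at 10% | Rule 2 threshold | Rule 2 not met at 10% | Rule 2 met at 25% |
|---|---|---|---|---|---|
| 7 | 93.2% | 52.2% | 2 | 85.0% | 55.5% |
| 8 | 92.3% | 57.0% | 2 | 81.3% | 63.3% |
| 9 | 91.3% | 61.3% | 3 | 94.7% | 39.9% |
| 10 | 90.4% | 65.1% | 3 | 93.0% | 47.4% |
| 12 | 88.6% | 71.8% | 3 | 88.9% | 60.9% |
| 15 | 86.0% | 79.4% | 4 | 94.4% | 53.9% |
| 16 | 85.1% | 81.5% | 4 | 93.2% | 59.5% |

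**Rule 1.** At 8 vaccinees, 1 − 0.9^8 = 57.0%, about 24 points below the value at 16. The chance that a 10% event is not seen is 0.9^8 = 43.0%, against the less than 20% that the text implies. At 15 the probability is already 79.4%, so at a 10% rate 16 is the smallest size at which the statement is true. The rate at which rule 1 reaches an 80% chance is 1 − 0.2^(1/n): 18.2% at n = 8 and 9.6% at n = 16. The statement about a 1% rate is safe at every smaller size, because 0.99^n rises as n falls.

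**Rule 2.** The threshold moves in whole infants, so the probabilities jump. At exactly 8, the statement at 10% fails (81.3%) and the one at 25% holds (63.3%). At 9 the pattern reverses (94.7% and 39.9%). At 7 both fail.

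**Pooled statement in Section 11.4.** The more than 99% chance of seeing at least one event at a 10% rate is 1 − 0.9^48 = 99.4% for 48 vaccinees. At the permitted minimum of 8 + 8 + 16 = 32 it is 1 − 0.9^32 = 96.6%.

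**The case against.** The strongest reply is that nothing has been miscalculated. Section 9.10.5 names 16 per group twice, in the sentence introducing Figure 4 and in the figure title, and the bullets report what that figure shows. *A maximum of* 16 may then mean at the maximum size, and on that reading the figures are right. This stands as far as it goes: a reader might infer an arithmetic error, and the documents do not support that. But the reading leaves Section 9.10.5 without any probabilities for the size at which Amendment 4 permits escalation, so the same edit is needed.

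A second reply is that the holding rules do not authorise escalation. The IDMC must find no significant safety concern and give formal approval; it reviews unblinded data monthly and receives fatal, life-threatening and related SAEs within 48 hours; and a single rule 1 event still triggers a hold at any group size. All of this is correct and limits the consequence. It does not change the chance that an event occurs among 8 vaccinees at all.

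A third is that Section 11.4 addresses 8 per group. It does so for platelets only: the sample size for ruling out the stated fall "with 84% power when vaccination has no effect on platelet count is 16 infants per dose cohort (8 per group". Its general AE statements rest on "The sample size of 32 subjects per dose cohort/Step, randomized 1:1 to vaccine or placebo", that is, on 16 vaccinees. Rules 1a to 1c have no stated properties at 8.

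A reader might also infer that exactly two of the four statements fail in the smaller groups, and that the rule 2 failure is harmless because it only produces more holds. That is true at exactly 8. The protocol fixes only approximately 8, with minimization by center, and at 9 the rule 2 shortfall is in detection.

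**Conclusion.** The point holds in this form: the probabilities in Section 9.10.5 are correct for 16 per group, and the Amendment 4 wording extends them to sizes for which they are not true. The firm part is rule 1 at a 10% rate: 57.0% at 8 vaccinees (52.2% at 7, 61.3% at 9) against a stated value above 80%. The overstatement is in the direction that makes the smaller cohort look safer to rely on. For rule 2, the conclusion is only that its statements cannot be carried to smaller groups without naming the exact number of vaccinees.

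This assumes independent infants with a common rate, and an early close near the permitted minimum. If Steps 1 and 2 enrol 16 vaccinees each, the existing figures apply. Step 3 keeps about 16 and is unaffected. The documents do not support going further and concluding that the holding rules are wrong, that the sample size must rise, or that early escalation is unsafe. The passage should be corrected because it states a safety-detection property that the permitted design lacks.

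**What to change.** In Section 9.10.5:

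1. Delete *a maximum of* and label the four statements and Figure 4 as for exactly 16 subjects per group.
2. Add rule 1 for 8 vaccinees: 92.3% not met at a 1% rate, 57.0% met at a 10% rate.
3. Add a short table of rule 1 and rule 2 probabilities by exact number of vaccinees, for example 7 to 16. Do not give a single rule 2 figure for about 8, since one more infant moves the chance of meeting rule 2 at a 25% rate from 63.3% to 39.9%.

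Optionally, note in Section 11.4 that the pooled figure above 99% is for 48 vaccinees and is 96.6% at the permitted minimum of 32.

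The cost is three words removed, one line and a small table added, and perhaps one clause in Section 11.4. The stated detection for Steps 1 and 2 becomes less favourable. No holding rule, dose or sample size changes, and no further infants are needed.

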 - Epoch 002: follow-up starting at Visit 10 (Day 365) and ending at Visit 11 (Day 730).

Any safety, immunogenicity and disease surveillance data collected beyond Visit 9 (Day 60) will be collected in Epoch 002.

- Primary completion Date: Visit 9 (Day 60).
Refer to [glossary of terms](#) for the definition of primary completion date.
- End of Study: Last testing results released of samples collected at Visit 11 (Day 730).*

* Up to Visit 11 (Day 730), there will be monthly nasal swab to detect asymptomatic RSV infections during the RSV season and if following active or a passive surveillance contacts, a subject presents symptoms of RTI, a nasal swab will be collected.

Refer to [glossary of terms](#) for the definition of end of study.

- Study groups: throughout the three steps, infants will be randomized in two groups to receive either ChAd155-RSV vaccine or placebo ([Table 1](#)).

Table 1 Study groups and epochs foreseen in the study (Amended 10 December 2017)

Step	Study groups	Number of subjects*	Age (Min/Max)	Epochs	
				Epoch 001	Epoch 002
1	RSV-Ld	~ 16	12 months - 23 months	x	x
	Placebo-Ld	~ 16	12 months - 23 months	x	x
2	RSV-Md	~ 16	12 months - 23 months	x	x
	Placebo-Md	~ 16	12 months - 23 months	x	x
3	RSV-Hd	~ 16	12 months - 23 months	x	x
	Placebo-Hd	~ 16	12 months - 23 months	x	x

RSV-Ld: low dose ChAd155-RSV vaccine (5×10^9 vp); **RSV-Md:** middle dose ChAd155-RSV vaccine (1.5×10^{10} vp); **RSV-Hd:** high dose ChAd155-RSV vaccine (5×10^{10} vp).

***The target will be to enroll up to 96 RSV-seropositive infants aged 12 to 23 months at the time of first vaccination (unless the dose escalation IDMC decision can be made based on the evaluation of accumulating safety data on fewer subjects) to ensure that at least 64 infants receive two doses of study vaccine (ChAd155-RSV or Placebo) (see Section 5.1). Then the number of subjects at each step will be at least 16 (approximately 8 subjects per group) at steps 1 and 2 and 32 (approximately 16 subjects per group at step 3) (Amended 10 December 2017).**

Table 2 Study groups and treatment foreseen in the study

Treatment name	Volume administered	Vaccine/Product name	Study Groups					
			Step 1		Step 2		Step 3	
			RSV-Ld	Placebo-Ld	RSV-Md	Placebo-Md	RSV-Hd	Placebo-Hd
ChAd155 5x10 ⁹ vp	0.5 ml	ChAd155-RSV	X					
ChAd155 1.5x10 ¹⁰ vp	0.15 ml	ChAd155-RSV			X			
ChAd155 5x10 ¹⁰ vp	0.5 ml	ChAd155-RSV					X	
Placebo 0.5	0.5 ml	Formulation buffer S9b		X				X

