9.10.4. Dose-escalation and safety evaluations by iSRC and IDMC

The study will be conducted in a staggered manner to ensure maximum safety of the participating infants progressing sequentially through the 3 dose levels (Figure 1):

- **Step 1:** vaccination of *a maximum of* 32 infants (approximately 16 infants in the RSV-Ld group and approximately 16 infants in the placebo-Ld group). An iSRC will review all accumulating safety data three weeks after the start of vaccination in Step 1 and then about every three weeks (until the IDMC has reviewed all safety data up to 30 days after administration of Dose 2 in Step 3 (i.e. Day 60). The IDMC will review all accumulating reactogenicity and safety data monthly throughout the period of vaccination (up to 30 days after administration of Dose 2 in Step 3, i.e. Day 60). Dose escalation *to Step 2* will proceed after *completion of vaccination for 32* subjects, and in the absence of a *significant* safety concern detected by the IDMC in

the regular monitoring of accumulating safety data. *However, in the absence of a significant safety concern detected in the regular monitoring of accumulating safety data on at least 16 subjects, the IDMC may recommend for dose escalation to proceed without the requirement of enrolling and evaluating the full group size of 32 subjects. A subsequent dose escalation will proceed after administration of two doses of the vaccine to between a maximum of 32 to a minimum of 16 subjects in the absence of a significant safety concern detected by the IDMC in the regular monitoring of accumulating safety data.* It will be ensured that, as a minimum the IDMC will have reviewed safety data of at least 16 subjects for two doses (in Step 1) and given their formal approval prior to enrolling subjects to the next dose level (Step 2). **(Amended 10 December 2017)**

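### Section 9.10.5 words its holding-rule probabilities as covering up to 16 vaccinees per group, but at the permitted size of about 8, rule 1 detects a 10% rate 57.0% of the time, not more than 80%

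*Protocol*

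**What the plan says.** The Risk assessment text in Protocol Section 9.10.5 introduces Figure 4 as giving probabilities for 16 subjects per study group in every step. The caption repeats that basis: "Evaluations based on 16 subjects - Risk assessment curve for one formulation based on the proposed safety holding rules". Four statements follow. Each rule 1 (a to d) has a better than 85% chance of not being met at rates below 1%, and it "has more than 80% chance of being met for vaccination with a true incidence rate above 10" per cent. Each rule 2 (a to c) "has more than 90% chance of not being met for vaccination with a true incidence rate below 10" per cent, and "more than 60% chance of being met for vaccination with a true incidence rate above 25" per cent.

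Amendment 4 edited the sentence leading into these statements. It now reads *a maximum of* followed by "16 subjects per study group (Amended 10 December 2017". The four probabilities were not changed.

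The same amendment made the group size variable. The Table 1 footnote in Protocol Section 3 says that "the number of subjects at each step will be at least 16 (approximately 8 subjects per group) at steps 1 and 2", and the Synopsis says that "the number of subjects enrolled to the low and mid dose is between 16 and 32 subjects". Step 3 stays fixed at 32. Section 9.10.4 keeps a safeguard before each escalation: "as a minimum the IDMC will have reviewed safety data of at least 16 subjects for two doses", with formal approval before the next dose level is enrolled.

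**The concern.** A chance of seeing at least one event rises with the number of infants observed. If 16 is the maximum, the probability at 16 is the best that rule 1 can do, so it cannot serve as a lower bound for smaller groups. The amended sentence presents it as one, in the same amendment that makes groups of about 8 possible.

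The bullets are the only stated operating characteristics of the holding rules in either document. Rule 1 covers the gravest events: related death or life-threatening SAE, withdrawal after a Grade 3 event, hospitalisation for a solicited event, and bleeding with platelets below 50,000/mm³. A reader judging how well these rules protect infants in a first paediatric study would take the stated detection to apply at the size on which escalation may be approved. Section 11.4 does not correct this. Its own statement of more than 80% at a 10% rate is also for 16 vaccinees, and its calculation at 8 per group concerns platelet counts only.

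**Working it through.** Inputs:

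- Rule 1 threshold: at least 1 infant per group (Table 21).
- Rule 2 threshold: at least 25% and at least 2 infants per group (Table 22). Taking 25% of the infants in the group gives 4 of 16 and 2 of 8.
- Group sizes: 16 (Figure 4) and about 8 (Table 1 footnote, with 1:1 allocation).
- Rates: 1%, 10% and 25%, as in the bullets.

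Model: events independent across infants, X binomial(n, p), one evaluation.

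**The plan's figures at n = 16**

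- Rule 1 not met at 1%: 0.99^16 = 0.851.
- Rule 1 met at 10%: 1 − 0.9^16 = 0.815.
- Rule 2 not met at 10%: P(X ≤ 3) = 0.932.
- Rule 2 met at 25%: P(X ≥ 4) = 0.595. It passes 60% from a rate of about 25.15%, which fits a statement about rates above 25%.

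All four reproduce, so the underlying calculation is sound.

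**The same quantities at n = 8**

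- Rule 1 not met at 1%: 0.99^8 = 0.923.
- Rule 1 met at 10%: 1 − 0.9^8 = 1 − 0.4305 = 0.570.
- Rule 2 not met at 10%: P(X ≤ 1) = 0.9^8 + 8 × 0.1 × 0.9^7 = 0.4305 + 0.3826 = 0.813.
- Rule 2 met at 25%: 1 − (0.75^8 + 8 × 0.25 × 0.75^7) = 1 − (0.1001 + 0.2670) = 0.633.

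| Statement | Stated | n = 16 | n = 8 |
|---|---|---|---|
| Rule 1 not met at 1% | > 85% | 85.1% | 92.3% |
| Rule 1 met at 10% | > 80% | 81.5% | **57.0%** |
| Rule 2 not met at 10% | > 90% | 93.2% | **81.3%** |
| Rule 2 met at 25% | > 60% | 59.5% | 63.3% |

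The rate at which rule 1 reaches 80% detection solves 1 − (1 − p)^n = 0.80. This gives p = 1 − 0.2^(1/8) = 18.2% at 8 vaccinees and 1 − 0.2^(1/16) = 9.6% at 16.

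Between these sizes, rule 1 detection at 10% is 65.1% at 10 vaccinees, 71.8% at 12 and 77.1% at 14. Rule 2 does not move smoothly, because its threshold is a whole number of infants. At 9 vaccinees the threshold is 3, which gives 94.7% not met at 10% and 39.9% met at 25%. The rule 2 values at 8 should therefore not be read across to nearby sizes.

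**The case against.** The strongest reply is that nothing was miscalculated. Figure 4 and its caption state a basis of 16, the numbers reproduce there, and the inserted words could be read as meaning at the maximum size. The first part stands: this is a wording and coverage fault. The second does not rescue the text, because the introduction to Figure 4 still says the basis applies in every step, and nowhere are holding-rule probabilities given at 8.

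A second reply is that the practical effect is small. That largely stands. Eight per group is a floor that the IDMC may choose to use. The IDMC sees unblinded data and must approve each escalation, a rule not being met does not itself trigger escalation, and several rules operate together while the bullets describe each one alone.

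A reader might also infer stronger conclusions that the documents do not support:

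- *That the bullets hold only for a single evaluation of 16.* Rule 1 does not depend on the number of reviews, and two of the four statements still hold at 8. At 15 vaccinees the rule 1 shortfall is trivial (79.4%).
- *That rule 2 becomes nearly blind at 8.* If 25% meant 25% of the planned 16, the threshold would stay at 4, and rule 2 would be met at a 25% rate only 11.4% of the time. That reading makes the separate floor of 2 infants redundant, so it is not the natural one. Table 22 could nonetheless name its denominator.
- *That repeated reviews break the 90% statement at 16.* This needs a denominator of infants to date and assumed look sizes, since the protocol gives review intervals but not numbers per look. Looks at 8 and 16 give 79.6%; looks at 10 and 16 give 90.1%; a denominator fixed at 16 leaves 93.2%.
- *That the rules are inadequate.* The shortfall is in the stated performance. Nothing here shows that the rules are wrong for a small staggered study.

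**Conclusion.** The point holds as a fault in the stated operating characteristics for Steps 1 and 2 when they stop early. At 8 vaccinees, rule 1 is met at a 10% true rate 57.0% of the time, so it misses that rate 43.0% of the time, compared with 18.5% at 16. This rests only on independent binomial events and the threshold of one infant.

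The rule 2 shortfall at 8 (81.3% against more than 90%) also requires the threshold to be 25% of the infants in the group. It is conservative: it means more holds at a 10% rate, and a hold leads to IDMC review and possible continuation. The smaller group size does not touch Step 3. The rule 2 denominator and the effect of repeated reviews are secondary clarifications.

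**What to change.** In Section 9.10.5, delete *a maximum of* and say that the existing four statements apply to 16 vaccinees. Add a line for Steps 1 and 2 at 8 vaccinees:

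- Rule 1: 92.3% not met at a 1% rate; 57.0% met at a 10% rate.
- Rule 2: 81.3% not met at a 10% rate; 63.3% met at a 25% rate.

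A short note saying what the 25% in Table 22 is a percentage of would be a useful secondary addition. If repeated-review figures are ever added, their look sizes should be labelled as assumptions.

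No holding rule or sample size changes. The only downside is a less favourable stated detection figure for small groups.
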